8.3. Vital Signs

Vital sign measurements include systolic and diastolic blood pressure, temperature, heart rate and respiratory rate. Vital signs are to be performed on Day 1, and prior to all PK sampling.

These measurements are summarised and summary statistics of the measurements by visit and change from baseline will be presented by dose group and overall.

8.4. Clinical Laboratory Parameters

8.4.1. Overview of Planned Clinical Laboratory Analyses

Clinical safety laboratory assessments including hematology, clinical chemistry, methemoglobin and additional parameters and screening tests are reported before the first dose of study drug and at Day 8 (and additionally at Day 3 for hematology).

Summaries of laboratory results and changes from baseline will be provided by visit. A listing displaying clinically relevant drops in hemoglobin by dose group will also be provided.

[Table 4](#) provides an overview of the planned analyses, with further details of data displays being presented in [Appendix 15: List of Data Displays](#).

Table 4 Overview of Planned Clinical Laboratory Analyses

Endpoint / Parameter/ Display Type	Absolute			Change from BL		
	Summary		Individual	Summary		Individual
	T	F	L	T	F	L
Chemistry						
Chemistry Data by Time	Y	Y ³				
Chemistry Changes from Baseline				Y		
Chemistry Laboratory Abnormalities ¹	Y		Y			
Clinical Chemistry Profile Plots		Y ²				
Hematology						
Hematology Data by Time and Sex	Y	Y ³				
Hematology Changes from Baseline by Time and Sex				Y	Y ³	
Hematology Laboratory Abnormalities ¹	Y		Y			
Hemoglobin Categories ⁴ of Change from Baseline by Time				Y		
Hemoglobin Categories ⁴ of Change from Baseline by Time and Sex				Y		
Maximum Fall in Hemoglobin Over First 10 Days					Y	
Mean Change in Hemoglobin Over First 10 Days ⁴				Y		
Hematology Profile Plots ⁵		Y				
Hepatobiliary (Liver)						
Liver Monitoring/Stopping Event Reporting	Y		Y			
Liver Biopsy Details	Y					
Liver Imaging Details	Y		Y			
Medical Conditions for Subjects with Liver Stopping Events			Y			
LFT Profile Plots ⁶		Y				
LFT Abnormalities		Y				
Maximum LFTs		Y				
LFT Changes from Baseline		Y				

NOTES:

- T = Table, F = Figures, L = Listings, Y = Yes display generated
- Summary = Represents TFL related to any summaries (i.e. descriptive statistics) of the observed raw data.
- Individual = Represents FL related to any displays of individual subject observed raw data.
- ¹ Abnormalities refer to values outside of the clinical concern range (F3) for the tables, and either outside of the clinical concern range (F3) or with a change from baseline of clinical concern (F2) for the listings, as defined in Section 10.8.1.
- ² Only for subjects with >3 ULN in ALT or AST or change from baseline in urea or creatinine >50%.
- ³ Boxplots for Hemoglobin, WCC, Platelets, ALT, AST and Creatinine. Change from baseline boxplot for Hemoglobin only.
- ⁴ Categories defined as <=20 g/L, >20 g/L to <=30 g/L, > 30 g/L ⁵ See Section 8.4.2
- ⁵ Individual plots for all subjects at each interim analysis. At SAC, only for subjects with a >30g/L decline from baseline hemoglobin or and found to be G6PD deficient; see Section 8.4.2.
- ⁶ Individual plots for all subjects at each interim analysis. At SAC, only for subjects with >3 ULN in ALT or AST
- All scheduled visits should be included in the tables and figures.
- Data recorded at unscheduled assessments will not be included in tables and figures (with the exception of being used in establishing maximum/minimum changes post baseline) but will be listed.

- Change from baseline is defined in Section [10.5.2](#).

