10.3. Appendix 3: Assessment Windows

10.3.1. Definitions of Assessment Windows for Analyses

Domain	Parameter (if applicable)	Target	Analysis Window		Analysis Timepoint
			Beginning Timepoint	Ending Timepoint	
Safety, PK, Efficacy	All	Day 1	Day -2	Day 1	Day 1
Safety, Efficacy	All except PK	Day 3	Day 3	Day 5	Day 3
Safety, PK, Efficacy	All	Day 8	Day 6	Day 10	Day 8
Safety, PK, Efficacy	All	Day 15	Day 12	Day 18	Day 15
Safety, PK, Efficacy	All	Day 29	Day 24	Day 34	Day 29
Safety, PK, Efficacy	All	Day 60	Day 50	Day 70	Day 60
Safety, PK, Efficacy	All	Day 90	Day 80	Day 100	Day 90
Safety, PK, Efficacy	All	Day 120	Day 110	Day 130	Day 120

For all data summarised by visit, the nominal visit description will be used. Unscheduled and withdrawal visit data will be slotted into a scheduled visit window, but the data will only be included in summaries and figures if no scheduled visit exists within the window. If there are multiple assessments within the same window which are not unscheduled visits, the earliest results will be used in the summaries. If only unscheduled visits are included in the same window, the earliest of these results will be used in summaries and figures.

For derivations of the maximum/minimum value/change post-baseline, then all data will be considered, regardless of whether or not it slotted to a scheduled window.

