10.6. Appendix 6: Derived and Transformed Data

10.6.1. General

Multiple Measurements at One Time Point

 If there are multiple assessments within the same window which are not unscheduled visits, the earliest results will be used in the summaries. All values will be listed. Subjects having both High and Low values for Normal Ranges at any post-baseline visits for safety parameters will be counted in both the High and Low categories of “Any visit post-baseline” row of related summary tables. This will also be applicable to relevant Potential Clinical Importance summary tables.
Study Day

 Study Day 1 is defined as the day the dose of study medication was taken. Study Day >1 calculated as the number of days from study Day 1 date: 
 Ref Date = Missing → Study Day = Missing Ref Date < Study Day 1 date → Study Day = Ref Date – study Day 1 date Ref Date ≥ Study Day 1 date → Study Day = Ref Date – (study Day 1 date) + 1
Cohort

 A subject’s cohort can be determined based on the date of study medication as follows: 
 Cohort 1 – Date of study medication <05-Jan-2018 Cohort 2 – Date of study medication ≥05-Jan-2018 and <26-Feb-2019 Cohort 3 – Date of study medication ≥26-Feb-2019

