10.8. Appendix 8: Values of Potential Clinical Importance

10.8.1. Laboratory Values

Element	Reporting Detail
F1 flag	
 Denotes a value that falls outside the normal range. Used by the laboratory and provided directly by the site for inclusion on the database.
F2 flag	
 Denotes a value that has increased or decreased from baseline by more than a specified amount. Defined below
F3 flag	
 Denotes a value that falls outside an extended normal range. This range is independent of any change from baseline or other values. F3 range is calculated as: 
 Absolute: pre-specified limits. Proportional: upper and lower limits are defined by multiplying the normal range limits by different factors Defined below
General	
 If a subject has both 'high' and 'low' values flagged for a parameter during the study, they will be reported once under each category.

Hematology				
Laboratory Parameter	Units	Category	Clinical Concern Range	
			Low Flag (< x)	High Flag (>x)
Hemoglobin	G/L	F2	Max(baseline – >30 g/L, ≥30% decline from baseline)	
Platelet count	10 ⁹ /L	F3	50	
Lymphocytes	10 ⁹ /L	F3	0.5	4
Eosinophils	10 ⁹ /L	F3		1.5
Reticulocytes count	10 ¹² /L	F3		1xULN

Clinical Chemistry				
Laboratory Parameter	Units	Category	Clinical Concern Range	
			Low Flag (< x)	High Flag (>x)
Creatine kinase (CPK) ^a	IU/L	F3		5x ULN
Creatinine ^a	μmol/L	F2		3x baseline
		F3		3x ULN

Clinical Chemistry				
Laboratory Parameter	Units	Category	Clinical Concern Range	
			Low Flag (< x)	High Flag (>x)
Urea (BUN) ^b	mmol/L	F3		11.067
Alanine aminotransferase	IU/L	F3		3x ULN
Aspartate aminotransferase	IU/L	F3		3x ULN
Total bilirubin	μmol/L	F3		1.5x ULN
Indirect bilirubin	μmol/L	F3		1.5x ULN
Alkaline phosphatase	IU/L	F3		2.5xULN

a. CTC AE criteria

b. FDA industry toxicity grading scale for healthy volunteer adults and adolescents in preventative vaccine trials

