3.24.		Safety	LB2	Summary of Worst Case Chemistry Results Relative to Potential Clinical Importance (PCI) Criteria Post-Baseline Relative to Baseline		SAC
Laboratory: Hematology						
3.25.	3.12	Safety	SA11	Summary of Hematology Data by Time and Sex	Add sex column	IA1, IA2, SAC
3.26.	3.13	Safety	SA12	Summary of Change from Baseline in Hematology Data by Time and Sex	ICH E3 Add sex column	IA1, IA2, SAC
3.27.		Safety	LB17	Summary of Worst Case Hematology Results Relative to Potential Clinical Importance (PCI) Criteria Post-Baseline Relative to Baseline	ICH E3	SAC
3.28.		Safety	SA13	Summary of Categories of Change from Baseline Hemoglobin (G/L) Data by Time		SAC
3.29.	3.14	Safety	SA13	Summary of Categories of Change from Baseline Hemoglobin (G/L) Data by Time and Sex	Add sex column	IA1, IA2, SAC
3.30.		Safety	SA14	Summary of Hemoglobin Declines over First 10 Days		SAC
3.31.		Safety	SA14	Summary of Hemoglobin Declines over First 10 Days by Sex	Add sex column	SAC
Hepatobiliary (Liver)						
3.32.		Safety	LIVER1	Summary of Liver Events Assessment	IDSL	SAC

Safety: Tables						
No.	IA No.	Population	IDSL / Example Shell	Title	Programming Notes	Deliverable
3.33.		Safety	LIVER2	Summary of Time on Treatment Before Liver Event		SAC
3.34.		Safety	LIVER3	Summary of Liver Biopsy Details		SAC
3.35.		Safety	LIVER4	Summary of Liver Imaging Details		SAC
	3.15	Safety	LIVER10	Summary of Hepatobiliary Laboratory Abnormalities	Only include rows for: - ALT \geq 5xULN - ALT \geq 3xULN - ALT \geq 3xULN and Bilirubin \geq 2xULN (>35% direct) or INR>1.5, if measured.	IA1, IA2
Vital signs						
3.36.		Safety	VS1	Summary of Absolute Values in Vital Signs by Visit	ICHE3 Include Systolic Blood Pressure, Diastolic Blood Pressure, Mean Arterial Blood Pressure, Heart Rate, Respiratory Rate and Temperature	SAC
3.37.		Safety	VS1	Summary of Change From Baseline in Vital Signs by Visit	ICHE3 Include Systolic Blood Pressure, Diastolic Blood Pressure, Mean Arterial Blood Pressure, Heart Rate, Respiratory Rate and Temperature	SAC

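### The hemoglobin category tables use absolute bands only, so qualifying falls at baselines of 80–100 g/L sit in the middle band, and Figure 3.9 plots only children with a large fall

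*SAP*

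**What the plan says.** Protocol section 3 lists clinically relevant Hb drops as a key safety endpoint, and section 4.6.1 marks hemolysis as the primary risk. Sections 4.6.1 and 7.5.1.1 define a protocol-specific serious event with three limbs: a relative fall of 30%, an absolute fall of 3 g/dL, or Hb below 6 g/dL. Entry requires a screening Hb of at least 8 g/dL (5.1).

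The SAP handles Hb falls in several displays:

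- **Tables 3.28–3.29** summarize change from baseline by visit. The note to SAP Table 4 reads "Categories defined as <=20 g/L, >20 g/L to <=30 g/L, > 30 g/L". The same note is attached to the first-10-days row of Table 4, which appears to correspond to Tables 3.30–3.31, "Summary of Hemoglobin Declines over First 10 Days", the second of them by sex.
- **Table 3.27** is titled "Summary of Worst Case Hematology Results Relative to Potential Clinical Importance (PCI) Criteria Post-Baseline Relative to Baseline". The only potential-clinical-importance rule for Hb in SAP 10.8.1 is a change-from-baseline (F2) flag: "Max(baseline – >30 g/L, ≥30% decline from baseline". Yet note 1 to Table 4 says "Abnormalities refer to values outside of the clinical concern range (F3) for the tables" and keeps F2 for the listings. Hb has no F3 limit.
- **Figure 3.9** (SAP 8.4.2 and 10.15.7) plots G6PD enzyme activity against maximum Hb fall, one page per dose group, only for children whose fall exceeds 30 g/L or reaches 30%.
- **Unscheduled values**: the Table 4 notes state "Data recorded at unscheduled assessments will not be included in tables and figures", with an exception for maximum and minimum changes. SAP 10.3.1 adds that "the data will only be included in summaries and figures if no scheduled visit exists within the window".

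**The concern.** SAP 8.4.2 and the F2 flag both recognize a 30% fall as important, but the category tables do not. A percentage rule and an absolute rule agree only when the baseline is high enough. Children who enter anemic have the least reserve, and for them the two rules part. A reader of Tables 3.28–3.29 who takes the top band as the number of children with a protocol-defined fall would get too small a number in exactly that group. Table 3.27 might supply the count, but the SAP gives opposite signals on whether Hb is in it. The Hb below 6 g/dL limb is in no SAP flag and no specified laboratory display.

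Figure 3.9 is a separate matter. A child enters the plot only if the plotted outcome is already large. Children with the same G6PD activity and a small fall are invisible, so the figure cannot show whether the fall varies with G6PD activity.

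**Working it through.** The plan gives no figure to reproduce here; the 60 children are a feasibility number (protocol 9.2).

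**Inputs, in g/L.** Lowest eligible Hb 80 (protocol 5.1). Rule from protocol 7.5.1.1, reading its misprinted connecting word as *or*: with baseline B and fall f, a child qualifies if f > 30, or f ≥ 0.30 × B, or B − f < 60. Middle band in Tables 3.28–3.29: f above 20 and up to 30.

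**Step 1, the relative limb.** 0.30 × B ≤ 30 when B ≤ 30/0.30 = 100. Above 100 g/L a 30% fall always exceeds 30 g/L, so the top band already equals the fall rule.

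**Step 2, the Hb below 60 limb.** It is reached before a 30% fall only when 0.7 × B < 60, that is B < 60/0.7 = 85.7.

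**Step 3, the lowest band.** At B = 80, a fall of 20 leaves Hb at 60, which is not below 60, and 0.30 × 80 = 24 is not reached. No qualifying fall sits in the lowest band.

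**Step 4, the middle band.** Whole-g/L falls 21 to 30 (ten values):

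| Baseline | 30% of baseline | Fall giving Hb < 60 | Qualifying falls | Count of ten |
|---|---|---|---|---|
| 80 | 24.0 | > 20 | 21–30 | 10 |
| 83 | 24.9 | > 23 | 24–30 | 7 |
| 85 | 25.5 | > 25 | 26–30 | 5 |
| 90 | 27.0 | > 30 | 27–30 | 4 |
| 95 | 28.5 | > 35 | 29–30 | 2 |
| 100 | 30.0 | > 40 | 30 | 1 |
| 101 | 30.3 | > 41 | none | 0 |

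At baseline 80, the 30% limb alone gives 7 of the 10 (falls 24 to 30).

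**Step 5, an example outside every laboratory rule.** Baseline 82, lowest value 59: the fall is 23 g/L, and 23/82 = 28%. It meets the Hb below 60 limb. It is not in the top band and does not enter Figure 3.9. The F2 limit is max(82 − 30, 0.7 × 82) = 57.4, and 59 is not below it.

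**Step 6, the protocol's two wordings.** Section 4.6.1 says at least 3.0 g/dL; section 7.5.1.1 says more than 3 g/dL. Under the first, a fall of exactly 30 g/L qualifies at any baseline and still lands in the middle band. Section 7.5.1.1 names the first 15 days; section 4.6.1 names no window.

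**Step 7, size.** The documents do not give the share of children with baseline 80–100 g/L. At an assumed 10%, 25% or 50% of 60, that is 6, 15 or 30 children. With an assumed 1% to 10% rate of large falls, the range is 6 × 0.01 = 0.06 to 30 × 0.10 = 3 children, even if every such fall lands in the middle band.

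**Step 8, Figure 3.9.** With the same assumed rates of 1%, 5% and 10%, 60 children give on average 0.6, 3 or 6 points, spread over up to five dose-group pages (SAP 10.5.1).

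**The case against.** A reader might infer that the SAP holds no laboratory-derived count at all, or that the number could come only from site-reported events or a hand count of Listings 14–15. The documents do not support either. Table 3.27's title points to a count of the F2 rule. Figure 3.9 isolates the two-limb cases from measured Hb by dose group, up to the Day 8 visit, and at the final analysis Figure 3.11 gives each such child a profile plot. With 60 children, counting these by hand is easy.

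Nor are unscheduled values dropped throughout. They are kept out of by-visit tables when a scheduled visit exists in the window, but they count towards maximum and minimum changes. A scheduled reading that prompts a repeat is itself in the by-visit table.

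The protocol rule is also a reporting rule, so the serious-event tables and Table 3.20 are natural places for these cases. That stands, but those tables depend on what sites report, and Table 3.20 also on a sponsor review of terms. The protocol does not define the key endpoint as this three-limb rule; however, the SAP's own 30% criterion is enough to show the gap in the bands.

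On Figure 3.9, the SAP never says that it estimates a relation, and its symbols classify large-fall cases by genotype. Fair, but plotting all children keeps that use and adds the comparison that is missing.

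Finally, the mock shells are not in the documents, so a suitable row inside Tables 3.27–3.31 cannot be ruled out. The SAP text specifies none.

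**Conclusion.** The point holds in limited form and should be addressed. Tables 3.28–3.29 pool qualifying with non-qualifying falls at baselines of 80–100 g/L. The SAP contradicts itself on whether Table 3.27 includes Hb. The Hb below 6 g/dL limb is in no flag or specified laboratory display; beyond the 30% rule it adds children only at baselines of 80 to below 85.7 g/L. Figure 3.9 cannot show whether the fall varies with G6PD activity.

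The number of children affected is probably small: 0.06 to 3 under the assumptions above, none of which the documents supply. No event is lost, since Listings 14–15, Figures 3.9 and 3.11 and the adverse-event tables would between them show these children. The primary PK endpoint is unaffected. Confidence is medium because the shells are unseen.

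**What to change.** First reconcile protocol 4.6.1 and 7.5.1.1 on the wording and time window of the Hb criterion; no threshold is proposed here. Then:

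1. In Tables 3.28–3.29 or 3.30–3.31, add a row for any visit after baseline, from the worst scheduled or unscheduled Hb. Count children who meet each limb and any limb of the protocol-defined fall, by dose group and overall. SAP 10.6.1 already uses such a "row of related summary tables. This will also be applicable to relevant Potential Clinical Importance summary tables", and 10.3.1 already allows all data for maximum and minimum changes.
2. Amend note 1 to Table 4 so that Table 3.27 includes the Hb F2 criterion, and add the protocol's Hb below 6 g/dL limb as a flag in 10.8.1.
3. In 8.4.2 and Figure 3.9, plot all treated children, mark those meeting the criterion and keep the genotype symbols. Most added points will be in the not-genotyped group. Footnote that eligibility truncates G6PD activity at 70% of the site median.

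Editorial only: name the listing of Hb drops promised in 8.4.1 or point to Listings 14–15, and align note 5 to Table 4 with the 30% limb in 8.4.2.

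The cost is SAP wording and minor programming on data already collected, with slightly busier displays.

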8.4.2. Hemoglobin Declines and Related Laboratory Parameters

For all subjects with a drop in hemoglobin >30 g/L or $\geq 30\%$, G6PD enzyme activity will be plotted against maximum drop in hemoglobin up to and including the Day 8 visit, with separate pages for each dose group. Within the plot, different symbols will be used for the following categories:

- subjects who were G6PD genotyped and had a mutation classified as World Health Organization (WHO) class 1
- subjects who were G6PD genotyped and had a mutation classified as WHO class 2 or 3
- subjects who were G6PD genotyped and had a mutation of unknown significance
- subjects who were G6PD genotypically normal or had a mutation classified as a normal variant (WHO class 4)
- subjects who were not G6PD genotyped or did not have an evaluable genotyping result

Individual profile plots for all subjects at each interim analysis. For SAC, if a subject has a >30 g/L or $\geq 30\%$ decline from baseline hemoglobin or is found to be G6PD deficient, a hematological profile plot will be produced for the subject. This will display their hemoglobin, absolute reticulocyte, methemoglobin and bilirubin results (total and indirect bilirubin on same plot) at each visit. The subject ID, treatment group, sex, age, weight and G6PD status should be included as a header for each subject's plot.

8.5. Pharmacokinetic Analyses

8.5.1. Overview of Planned Pharmacokinetic Analyses

The pharmacokinetic (PK) analyses will be based on the Pharmacokinetic population, unless otherwise specified.

8.5.2. Drug Concentration Measures

Refer to [Appendix 5: Data Display Standards & Handling Conventions](#) (Section [10.5.3](#) Reporting Process & Standards).

8.5.3. Pharmacokinetic Parameters

PK parameters will be estimated based on POP PK model. See [Appendix 12](#) for more details.

8.5.4. Population Pharmacokinetic (PopPK) Analyses

- The primary goal of this analysis is to characterize the population pharmacokinetics of tafenoquine (TQ) administered orally in subjects with *P. vivax* malaria.

- The influence of subject demographics, baseline characteristics, including disease activity, and co-medication on the pharmacokinetics of TQ in this population will be investigated.
- A summary of the planned population pharmacokinetic analyses are outlined below:
 - Drug plasma concentration-time data will be subjected to nonlinear mixed effects modelling using the program NONMEM to develop a population PK model.
 - Individual post-hoc estimated PK parameters will be summarised descriptively.
 - To support this analysis a NONMEM data file will be generated.
 - The details for the dataset specifications are provided in [Appendix 13: Population Pharmacokinetic Analyses](#) with detailed methodology for the analysis.

8.6. Pharmacodynamic Analyses

Not applicable

8.7. Pharmacokinetic / Pharmacodynamic Analyses

Not applicable

8.8. Evaluation of Microsampling

The relationship between venous blood sampling concentrations and capillary microsampling concentrations will be explored using the PK population.

A scatterplot comparing the venous blood plasma concentrations and the microsampling blood concentrations for all subjects, at all timepoints will be produced. In addition, the correlation between the methods will be calculated and presented in the same plot. The correlation will be calculated separately for each quartile, according to the concentration range observed.

To quantify the level of agreement between the blood sampling methods, a Bland-Altman plot will be produced [Bland, 1999]. The plot will display average concentration (x-axis) versus the concentration ratio (microsampling concentration/venous concentration) (y-axis). The following reference lines will be included in the plot

- Mean concentration ratio (bias)
- Mean concentration ratio \pm 5% (interim analysis 1 only)
- Mean concentration ratio \pm 15% (interim analysis 2 and SAC only)
- Limits of agreement calculated as: mean concentration ratio \pm 1.96 x SD

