7.6. Pharmacokinetics

Blood samples for PK analysis of TQ will be collected at the time points indicated in the Time and Events Table (Section 7.1). The Day 3 sample should be taken 24-96 hours after TQ dosing and a concurrent set of vital signs should also be obtained. Sample(s) of 1 mL blood will be collected (via venipuncture) into blood tubes and/or 70 µL blood (via finger or heel prick) will be collected into capillary tubes. Each sample will be centrifuged to produce plasma and the plasma transferred into a tube for shipping to a central laboratory for analysis. The actual date and time of each blood sample collection will be recorded. The timing and collection of PK samples may be altered and/or PK samples may be obtained at additional time points to ensure sufficient PK monitoring. In addition, concentrations of CQ will be determined. Details of the PK blood sample collection (both venipuncture and microsampling), processing, storage and shipping procedures are provided in the SRM.

Evaluation of correlation between venous and microsampling data will be made at each interim analysis. If microsampling data is deemed adequately representative of venous blood samples, any further PK sampling will switch predominantly to microsampling. However, up to two out of the four planned PK samples per subject may still be collected by both venous and microsampling methods. This will be as a back-up given the primary objective of this study is to adequately characterize the PK of TQ in the pediatric population. The PK data hence is of critical value. In the event that microsampling data is deemed an inadequate representation of venous samples, any further PK sampling will be only by venous sampling.

The sampling strategy of four PK samples per subject is designed to be sparse but adequately characterize the PK of TQ in the pediatric population. These four samples per subject will be reduced to two samples per subject at the earliest interim analysis once reliable characterization of TQ PK has been achieved.

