3. PLANNED ANALYSES

3.1. Interim Analyses

Up to two main interim analyses have been planned so that serial but sparse PK sampling (i.e., 4 PK timepoints) may be reduced at the earliest opportunity. The first interim analysis will take place after a total of at least 16 subjects in the main cohort have PK evaluable data or 12 months post study initiation, whichever comes first. The second interim analysis will take place after a total of at least 32 subjects in the main cohort have evaluable PK data or at 24 months post study initiation, whichever comes first. The second interim analysis will take place only if serial but sparse PK sampling is continued after the first interim analysis.

The interim analyses will be performed after the completion of the following sequential steps:

1. All required subjects (i.e. 16 or 32 subjects) have PK evaluable data as defined in the protocol (or 12/24 months post study initiation).
2. All required database cleaning activities have been completed and interim database release and database freeze has been declared by Data Management.

If it is found that due to insufficient number of children being enrolled in the lowest weight band(s) the prediction intervals are wider in that lowest weight band, then further serial (but sparse) sampling may be limited to the children being enrolled in the lowest weight band. The analyses will then be repeated after next set of 4 subjects and so on until the TQ PK for that weight band are adequately characterized and the 95% interval within the targeted 55-162 $\mu\text{g}\cdot\text{hr}/\text{mL}$.

See [Appendix 12](#) for details about the population pharmacokinetic analysis.

The correlation between TQ PK data from venous sampling and capillary microsampling will be evaluated. Based on the emerging data, if deemed appropriate, further PK sampling of TQ in pediatric subjects will be limited predominantly to capillary microsampling to reduce the PK sampling burden on this highly vulnerable population. Agreement will be evaluated based on correlation and Bland-Altman analyses. Further details will be documented in the TAF113577 Interim Analysis Charter.

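### Venous-capillary correlation computed within concentration quartiles is not a measure of agreement, yet SAP 3.1 names correlation as a basis for the microsampling decision

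*SAP*

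**What the plan says.** Protocol 7.6 provides that "Evaluation of correlation between venous and microsampling data will be made at each interim analysis", and attaches a consequence: "If microsampling data is deemed adequately representative of venous blood samples, any further PK sampling will switch predominantly to microsampling". If microsampling is judged inadequate, further PK sampling is venous only.

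SAP 3.1 gives the basis for that judgement: "Agreement will be evaluated based on correlation and Bland-Altman analyses". It then defers: "Further details will be documented in the TAF113577 Interim Analysis Charter".

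SAP 8.8 specifies the displays. A scatterplot of the two methods "for all subjects, at all timepoints will be produced". Next, "In addition, the correlation between the methods will be calculated and presented in the same plot", followed directly by "The correlation will be calculated separately for each quartile, according to the concentration range observed". A separate paragraph reads "To quantify the level of agreement between the blood sampling methods, a Bland-Altman plot will be produced". That plot shows the capillary/venous ratio against the average concentration, with the mean ratio, lines at ±5% (first interim) or ±15% (second interim and final analysis) around that mean, and limits of agreement.

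Neither document states the type or scale of r, which method's values define the quartiles, how four quartile values are combined, or what value of r would be acceptable.

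**The concern.** Correlation depends on the spread of the concentrations as well as on the error between methods. Cutting the pairs into concentration quartiles removes most of the spread and leaves the error unchanged, so r drops although the methods agree exactly as well as before. Each quartile also holds few pairs, and those pairs are pooled over children and visits as if independent. In the other direction, r is unchanged if every capillary value is, say, 30% too high.

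The statistic can therefore fall when agreement is good and stay high when the methods are biased. It is one of two named inputs to a choice about how children are sampled for the rest of the trial, in a study whose primary endpoint is PK.

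**Working it through.** The plan states no r, threshold or sample size for the method comparison, so there is no figure of its own to reproduce.

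**Inputs from the documents**
- PK model: Protocol Appendix 9, Table 7 (A 0.8586, B 0.4813, Alpha 0.4380, Beta 0.0415, KA 3.3073, pBWT 0.5217; log-SDs 0.2766, 0.1695, residual 0.2657).
- Weights: log-normal, log-mean 3.36, log-SD 0.66 (same appendix).
- 16 children at the first interim (SAP 3.1), Days 3, 15, 29 and 60 (Protocol 9.2.1), and the pre-Amendment 2 doses (SAP 2.3).

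Check that the model is read correctly: (0.8586/0.4380 + 0.4813/0.0415 − 1.3399/3.3073) × 24/1000 = 0.316 µg·h/mL per mg, matching Appendix 8.

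**Assumptions**
- Weights are truncated to 5–70 kg.
- Both methods are unbiased, with equal log-normal error.
- The model residual is shared by both samples of a pair. This widens the range and so favours quartile r.
- r is Pearson on the raw scale.
- Between-method scatter is set at two levels:
  - 95% of ratios within about ±15%: ratio CV = 15/1.96 = 7.65%.
  - 10% CV per method: ratio CV = √2 × 10 = 14.1%, so 95% of ratios within about 1.96 × 14.1 = ±28%.

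**Pairs per quartile.** 16 × 4 / 4 = 16 if all four days are paired; 16 × 2 / 4 = 8 if two are.

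**Hand check of the mechanism.** On the log scale, r ≈ V/(V + e²), where V is the variance of log concentration in the set and e is the error SD per method. In the simulated data the central 95% of concentrations runs from about 6 to 420 ng/mL, and the second quartile from about 26.3 to 64.0.
- Pooled: SD ≈ ln(420/6)/3.92 = 1.08, V = 1.17.
- Second quartile, taken as uniform: SD ≈ ln(64.0/26.3)/√12 = 0.257, V = 0.066.
- At 10% CV per method (e² = 0.010): pooled r ≈ 0.99, second quartile 0.066/0.076 = 0.87.
- At ±15% (e = 0.0765/√2, e² = 0.0029): second quartile 0.066/0.069 = 0.96.

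The error is the same in both sets. Only the range has changed.

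**Simulation, 16 children, medians over replicates**

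| Days paired | Scatter | Pooled r | Quartile r |
|---|---|---|---|
| 3, 15, 29, 60 | ratios within about ±15% | 0.995 | 0.96–0.99 |
| 3, 15, 29, 60 | 10% CV per method | 0.98 | about 0.87–0.96 |
| 15, 29 | ratios within about ±15% | 0.99 | middle two about 0.82–0.85 |
| 15, 29 | 10% CV per method | 0.96 | middle two about 0.5–0.66 |

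The second decimal moves slightly with the rule for forming quartiles. With wide scatter and two paired days the rule matters more: the middle-quartile values are lower when quartiles are cut on the mean of both methods than when cut on the venous value.

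**Noise.** An observed r of 0.80 on 8 pairs gives z = 1.099 ± 1.96/√5, a 95% CI of 0.22 to 0.96. On 16 pairs it is 1.099 ± 1.96/√13, or 0.50 to 0.93. Both treat pairs as independent, which repeated samples from one child are not.

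**Bias.** Multiplying all capillary values by a constant leaves r unchanged. With a 30% bias and a 5% ratio CV, the simulated pooled r is 0.998 and the quartile values are 0.98 to 0.99.

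**The case against.** Four points can fairly be made for the plan.

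1. *The effect may be small.* With four paired days and ratios inside a ±15% band, quartile r stays at about 0.96 to 0.99. This stands. The large drops need wider scatter or fewer paired days. At 10% CV per method the ratios spread to about ±28%, beyond the SAP's ±15% lines, so part of a low r there reflects real scatter.

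2. *The two-day pairing is not in the plan for the first interim.* Protocol 7.6 mentions up to two of four paired samples only for the period after microsampling is accepted, and Days 15 and 29 are the reduced schedule once full sampling stops. This stands too: the number of pairs before the first interim is not stated, so that scenario is one end of a range.

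3. *The Bland-Altman plot does the real work.* SAP 8.8 gives it the task of quantifying agreement, it is not split by quartile, its mean-ratio line would show a bias, and plotting ratio against concentration gives a visual check of concentration dependence. The sentence before the quartile rule can also be read as promising an overall r. This is a substantial safeguard, but partial: SAP 3.1 still lists correlation beside it, with no rule for the case where the two disagree.

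4. *No decision rule uses r.* A reader might infer that a valid capillary method would be rejected and the remaining children returned to venous-only sampling. The documents do not support that. They give no cut-off and no rule that the lowest quartile decides, and the Interim Analysis Charter is not among them. Nor would a rejection lose primary PK data, since venous sampling would continue; the cost would be sampling burden.

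**Conclusion.** The point holds as a defect in the chosen statistic. Quartile r is lowered by range restriction alone, is imprecise with 8 to 16 pairs, ignores clustering by child, and cannot see a constant bias. No threshold, whether in the charter or elsewhere, would turn it into a measure of agreement.

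Its size is uncertain. The loss is negligible to modest if all four days are paired and scatter is tight, and large in the middle quartiles if only two days are paired or scatter is wide. These figures rest on assumed scatter and pairing and on the Table 7 model.

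A reader might also conclude that replacing quartile r by one pooled r would solve the problem. It would not: the wide concentration range inflates the pooled value (0.96 or more in all four scenarios), and it is equally blind to bias.

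**What to change.** In SAP 8.8, replace the quartile-specific correlations with:
- the mean capillary/venous ratio and its 95% CI in each concentration quartile, allowing for repeated samples per child. Define quartiles by the mean of both methods, because cutting on one method's measured value distorts the ratio at the extremes;
- a regression of log(capillary/venous) on log mean concentration, with child as a random effect. This answers the question the quartiles seem meant to ask: does agreement change with concentration?

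In SAP 3.1, base the agreement judgement on the ratio bias and the limits of agreement. Any overall correlation or concordance coefficient should be labelled descriptive only, since both depend on the concentration range.

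The cost is a short change of SAP wording and a little more analysis, on data already planned. The drawback is that the intervals per quartile will be wide at the first interim, which shows openly how little 8 to 16 pairs can say.
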